Approximately 260 patients with squamous cell carcinoma of the oral cavity and oropharynx scheduled to receive a minimum total cumulative radiation dose of 55 Gy fractionated as 2.0-2.2 Gy per day and concomitant cisplatin chemotherapy given as a dose of 80-100 mg/m² (every third week) will be enrolled. Subjects will be randomized to receive either 1.5 mg/kg SGX942 or placebo given as a 4-minute IV infusion using an infusion or syringe pump. Blinded study drug will be started within 3 days after starting RT and continued twice a week (2-4 calendar days apart) through 2 weeks after completion of the RT. Efficacy will be assessed by oral examination at each treatment visit and then at the 3 through 6 weeks post-RT completion visits. OM will be evaluated using the WHO Grade system and performed by observers trained on these measurements. SOM is defined as a WHO Grade of \geq 3. The duration of SOM is defined as the first time the patient has a WHO Grade \geq 3 until the first time the patient has a WHO Grade of <3 with no subsequent readings \geq 3. Patients will be randomized (1:1; 1.5 mg/kg SGX942:placebo) using an interactive web response system (IWRS). Randomization will be stratified by site, presence of prophylactic gastrostomy feeding tube, and tumor human papillomavirus (HPV) status.

Routine clinical chemistry and hematology will be obtained at Screening/Baseline, then at 3, 6, and 9 weeks while receiving study drug, and then at the 4 and 6 week post-RT completion visit. The same type of scan initially used to stage the tumor (i.e., computed tomography [CT], magnetic resonance imaging [MRI] or positron emission tomography [PET]) will be repeated at 12 weeks and 12 months after completion of the radiation therapy and compared to the initial scan using the RECIST 1.1 criteria.

Number of Patients (planned):

260 patients (130 SGX942 treated and 130 placebo treated patients) will be enrolled.

Diagnosis and Main Criteria for Inclusion:

Inclusion Criteria

Patients must meet *all* of the following criteria in order to be eligible for enrollment:

- 1. Willing and able to understand and sign an informed consent
- 2. Males or females age greater than or equal to 18 years
- 3. Biopsy-proven squamous cell carcinoma of the oral cavity or oropharynx without distant organ metastases that has been evaluated for human papillomavirus (HPV)
- Scheduled to receive cisplatin chemotherapy of 80-100 mg/m² given every third week

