The primary analysis will be a log-rank test of the differences in the duration of SOM between the 1.5 mg/kg SGX942 and placebo treated groups. A log-rank test will be used to compare the AUC of the WHO Grade-time curve and the number of days to onset of OM. The incidence of SOM and UOM, percent of RECIST complete responders, percent of patients with presumed bacterial infections and severity of infections will be compared using chi-squared tests. The primary analysis population will be all patients receiving drug who have received enough radiation exposure to put them at significant risk of developing SOM (defined as a cumulative radiation dose of at least 55 Gy).

Original: 11 January 2017 Confidential

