In placebo patients whose tumors were human papillomavirus negative (HPV-), the median duration of SOM was 33 days compared to 11 days in those patients whose tumors were human papillomavirus positive (HPV+). In patients with HPV- tumors, SGX942 reduced the median duration of SOM in both the 1.5 and 6.0 mg/kg SGX942 dose groups by 76%. This was associated with a 73% reduction in the median AUC for the WHO Grade-time measurement in the 1.5 mg/kg SGX942 dose group and a 76% decrease in the 6.0 mg/kg SGX942 dose group. Similarly, relative incidence decreased by 22% in the 1.5 mg/kg dose group and 10% in the 6.0 mg/kg group.

The lowest dose tested, 1.5 mg/kg, was effective in reducing the duration of oral mucositis (OM) in head and neck cancer patients. At the request of the USA Food and Drug Agency (FDA) during study design, the 3.0 mg/kg dose of dusquetide was included primarily as a safety step in the dose escalation. Only 3 patients received this dose, hence, no effectiveness conclusions are possible for this dose. The results in the 6.0 mg/kg SGX942 dose group compared to the placebo group are inconsistent across the various measures of SOM and across the various subpopulations, suggesting that it is not as effective in ameliorating OM as the 1.5 mg/kg SGX942 dose. Decreased effectiveness at the 6.0 mg/kg dose level is consistent with findings in the Phase 1 study with SGX942, where anti-inflammatory activity was more prevalent at the lower dose level (Figure 3) [3].

In addition to the improvement in OM, a decrease in the rate of infections, particularly nonfungal (bacterial) infections was also observed (Table 3).

Confidential

Original: 11 January 2017 Amendment 1: 29 November 2017 Amendment 2: 22 January 2018

Amendment 3: 17 September 2019

Table 3: Reported Infections

Treatment Group	Placebo	1.5 mg/kg	6.0 mg/kg
	n = 38	n = 36	n = 19
All Infections: n (%) p-value compared to placebo	29	23	8
	(76%)	(64%)	(42%)
	—	0.311	0.018
Non-fungal Infection: n (%) p-value compared to placebo	17	10	4
	(45%)	(28%)	(21%)
	—	0.153	0.144
Serious Infection: n (%) p-value compared to placebo	8	7	3
	(21%)	(19%)	(16%)
	—	>0.999	0.735

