8.4. Randomization and Blinding

Patients will be randomized 1:1 to SGX942:placebo using a randomization code generated by an independent statistician. Randomization will be performed using an Interactive Web Response System (IWRS) in a double-blind fashion. Each vial of SGX942 and the identically appearing placebo vials will be supplied and labeled with a unique blinded identifying code. The IWRS will assign vial(s) of the appropriate study material to be used for each patient and each infusion using this blinded code.

Patients will be stratified at randomization by HPV status, presence of a gastrostomy tube at randomization, and study site.

[figure not shown]
Given the extremely short half life of SGX942 (minutes), it is anticipated that knowledge of whether the patient received placebo or SGX942 will rarely be needed. If, however, the PI and/or the primary care clinical team believe that this information is necessary to optimally treat an enrolled patient, the clinical data management team (DSG) should be contacted (24 hour/7 day availability) using the contact directions available in the eCRF portal. The study drug assignment for that patient will be determined and confirmation of the study drug received will be immediately sent.

Confidential

[figure not shown]

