12. STATISTICS

12.1. Overview

Complete details of analyses and relative order of importance of each analysis are more fully delineated in the Statistical Analysis Plan.

Given the anticipated non-Gaussian distribution of values for duration of OM, the severity-weighted OM calculations (AUC), and the days to onset of OM, treatment groups will be compared for these variables using a log-rank test of the differences in the duration of SOM between the SGX942 and placebo treated groups. The incidence of OM, percent of RECIST complete responders, and percent of patients with each category of infection will be compared using chi-squared tests. The primary analysis population will be patients who have received enough radiation exposure to put them at significant risk of developing SOM (defined as a cumulative radiation dose of at least 55 Gy).

Original: 11 January 2017 Amendment 1: 29 November 2017

Amendment 2: 22 January 2018 Amendment 3: 17 September 2019

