## 3 STATISTICAL CONSIDERATIONS

#### 3.1 SAMPLE SIZE CALCULATION

Sample size assessments are based on testing the hypothesis of superiority with a two-sample log rank test using the median duration of SOM, an equal allocation ratio, a 90% power (1- $\beta$ ), and an  $\alpha$  level of 0.05. In the Phase 2 clinical trial, the median duration of SOM was 30 days in the placebo group and 10 days in the 1.5 mg/kg SGX942 treatment group. Because of the variability of reported results for SOM in the patient population, a conservative assumption was made that the median duration of SOM among patients receiving a minimum of 55 Gy of cumulative radiation will be 13 days in the placebo group and 8

days in the SGX942 group. Using this assumption, approximately 95 evaluable patients per arm (190 patients total) were to be randomized.

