#### 9.1 ANALYSIS OF PRIMARY ENDPOINT

As detailed in Table 2, the clinical evaluation of mucositis will be performed and graded by trained study evaluators in accordance with the WHO Oral Mucositis Grading system at each study drug administration visit and for Week 3 through Week 6 post-RT.

SOM is defined as OM with WHO Grade  $\geq 3$ . The duration of SOM is defined as the number of days from the first WHO score  $\geq 3$  to the first day with a WHO score  $\leq 3$  with no further occurrence of a WHO score  $\geq 3$ . A log-rank test will be used to compare the duration of SOM of the two treatment groups.

Resolution of SOM is defined as the first assessment with a WHO score <3 with no further reports of a WHO grade of  $\ge 3$ . If the patient has not met the requirements for resolution of SOM by the 6-week post-RT visit, he/she will be considered censored at that visit (or the point of discontinuation from the study, if the patient discontinues prior to that time point). For statistical reasons, patients who do not experience SOM will be treated as having a duration of 0.01 days.

Possible scenarios for onset of SOM are displayed below in Figure 2, along with the derivation of duration of SOM.

[figure not shown]

Figure 2: Duration of SOM (Primary Analysis)

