#### 9.4.3 **Duration of UOM**

UOM is defined as a WHO score  $\geq$ 2. The duration of UOM is defined as the number of days from the first WHO score  $\geq$ 2 to the first day with WHO score  $\leq$ 2 with no further occurrence of WHO score  $\geq$ 2. A log-rank test will be used to compare the duration of UOM between the two treatment groups.

Resolution of UOM is defined as the first assessment with a WHO score <2 with no further reports of a WHO grade of  $\ge 2$ . If the patient has not met the requirements for resolution of UOM by the 6-week post-RT visit, he/she will be considered censored at that visit (or the point of discontinuation from the study, if the patient discontinues prior to that time point). For statistical reasons, patients who do not experience UOM will be treated as having a duration of 0.01 days.

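### Randomisation is stratified by HPV status, gastrostomy tube and site, but the primary log-rank test ignores the strata and no stratified, adjusted or by-HPV efficacy analysis is planned; this is an efficiency point, not a validity error

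*SAP*

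**What the plan says.** **Randomisation.** The protocol synopsis states: "Randomization will be stratified by site, presence of prophylactic gastrostomy feeding tube, and tumor human papillomavirus (HPV) status". Protocol 8.4 repeats it: "Patients will be stratified at randomization by HPV status, presence of a gastrostomy tube at randomization, and study site". Protocol 6.1 and SAP 2 agree.

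**Primary test.** No description names strata or covariates.
- Protocol synopsis: "The primary analysis will be a log-rank test of the differences in the duration of SOM".
- Protocol 12.1: "treatment groups will be compared for these variables using a log-rank test of the differences in the duration of SOM".
- SAP 9.1: "A log-rank test will be used to compare the duration of SOM of the two treatment groups".
- The sample size (SAP 3.1, matching Protocol 12.4) rests on "testing the hypothesis of superiority with a two-sample log rank test using the median duration of SOM".

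**Other efficacy analyses.** SAP 9.2 changes the definition of duration and keeps the method. SAP 9 repeats the assessments in other populations. Appendix 1 varies the missing-data rule and the pandemic handling. SAP 9.4.2 inherits the primary method, and SAP 9.4.3 states its own test: "A log-rank test will be used to compare the duration of UOM between the two treatment groups". The remaining comparisons use one-way ANOVA, chi-square or Wilcoxon tests. HPV status and tube reappear only among the baseline summaries in SAP 6. No reason is given for leaving them out of the efficacy analyses.

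**The concern.** Stratifying the randomisation by a prognostic factor balances that factor between arms. A test that ignores the factor still carries the between-stratum variation in its variance, although that variation can no longer favour either arm. The test then rejects too rarely under the null and, if the effect is similar across strata, loses power.

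The protocol's own Phase 2 account suggests that HPV status is such a factor. Protocol 4.5 gives placebo median durations of 33 days in HPV-negative and 11 days in HPV-positive patients. What is at stake is power at the planned effect, and whether a stratified estimate and an HPV breakdown are planned or would have to be added post hoc.

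**Working it through.** **1. The plan's own figure.** Inputs from Protocol 12.4 and SAP 3.1 and 3.3: medians 13 v 8 days, 1:1 allocation, two-sided 0.05, 90% power. With exponential durations the ratio is 8/13 = 0.615.
- Freedman: events = [(1 + 0.615)/(1 - 0.615)]² × (1.960 + 1.282)² = 17.64 × 10.51, which rounds up to 186.
- Schoenfeld: events = 4 × 10.51 / (ln 0.615)² = 42.03 / 0.2357, which rounds up to 179.

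The stated 190 is reproduced within about 3% by Freedman. The sample-size arithmetic is not in dispute, but it makes no allowance for HPV.

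**2. Simulation assumptions.** Exponential durations in two HPV groups; threefold HPV effect (33/11); group medians scaled so that the pooled placebo median is 13 days; 1:1 within HPV group; censoring at 42-77 days; HPV-negative share 30, 50 or 70%. The trial's HPV mix is not given. The sizes are 190 (stated), 229 (88% of 260, assumed) and 260.

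**3. Results.** Power in %, for HPV-negative shares 30/50/70%. Ratio means median duration, active over placebo.

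| Case | n | Plain | HPV-stratified |
|---|---|---|---|
| Common ratio 8/13 | 190 | 78/79/83 | 89/89/90 |
| Common ratio 8/13 | 229 | 86/85/89 | 94/93/93 |
| Common ratio 8/13 | 260 | 90/90/93 | 96/96/96 |
| HPV- 0.55, HPV+ 0.70 | 229 | 83/91/96.5 | 86/92/96.8 |
| HPV- 0.45, HPV+ 0.85 | 229 | 79/96/99.6 | 66/91/99 |

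Repeat simulations of the common-ratio case gave up to 84% for the plain test at 190, and gains of 5-9 points at 229. With a twofold HPV effect the gain is 3-4 points at 190 and 2-3 at 229; with a 1.5-fold effect it is about 1 point or less.

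**4. Type I error.** The plain test rejects in about 2.5-4% of null trials when HPV is balanced exactly, and in about 3.3-4.6% with sparse blocks within site, HPV and tube. The HPV-stratified test stays near 5%.

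**5. What Phase 2 implies for HPV-positive patients.** Protocol 4.5 gives pooled medians of 18 (placebo) and 9 days (1.5 mg/kg), and a 76% reduction in HPV-negative patients.
- HPV-negative share p: 0.5 = p × 2^(-18/33) + (1 - p) × 2^(-18/11) = 0.685p + 0.322(1 - p), so p = 0.49.
- HPV-negative active median: 33 × 0.24 = 7.9 days.
- HPV-positive active median m: 0.5 = 0.49 × 2^(-9/7.9) + 0.51 × 2^(-9/m), so m = 10.2 days and the ratio is 10.2/11 = 0.93 (0.81-1.06 allowing for rounding).

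With an HPV-positive ratio of 0.93 and pooled medians held at 13 v 8, power at 229 for HPV-negative shares 30/49/70% is 98/99/98% plain v 86/94/95% stratified. At an HPV-positive ratio of 1.0 and 30% HPV-negative it is 97.5% v 79%. The break-even HPV-positive ratio is about 0.67/0.70/0.74 for HPV-negative shares 30/50/70%.

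**6. Patients without SOM, entered at 0.01 days.** Assume 10% of HPV-negative and 30% of HPV-positive patients, equal by arm, at 229. The common ratio gives 60/65/76% v 74/77/82%, and the 0.45/0.85 case gives 54/87/98% v 47/79/97%. Levels fall but the ordering is unchanged.

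**7. Site.** The synopsis plans 50-60 centres. With two levels each of HPV and tube that is 200-240 cells for 260 patients. Stratifying on all three factors gave only 28-31% power at 190 under the common ratio (55 sites assumed).

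**The case against.** **The test is already fixed.** One two-group log-rank is named throughout, at a two-sided 5% level. A reader might infer that the choice of test has been left open, or that ignoring the strata inflates false positives. Neither is supported: the test is specified in advance, and it errs on the conservative side. What is absent is a rationale and any supporting stratified analysis.

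**The sign of the gain is uncertain.** Protocol 4.5 says that the drug seemed most effective where SOM was expected to last longest, and the back-solved HPV-positive ratio of 0.93 favours the plain test at every HPV mix tried. This stands as a real downside. The same section also says, however, that Phase 2 results were similar across subpopulations, naming HPV status, which supports a common effect. The planning calculation uses one pair of medians with no HPV-specific effect.

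**The gain may be small.** The threefold HPV effect comes from a Phase 2 trial with at most 43 placebo patients, not limited to every-third-week cisplatin. SAP 2 also allows up to 10% more enrolment. At 252 evaluable (88% of 286, assumed) the plain test has about 88-92% power under a common ratio with a threefold HPV effect, and 93-95% with a twofold effect. This limits the size of the point but does not remove it.

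**The change is late.** The DMC reviews unblinded interim data (Protocol 11.6) and has already recommended the increase to 260 (SAP 2). The interim method is not visible in the text supplied, and table shells are in a separate document that might hold an HPV breakdown. The fix therefore depends on what the interim look used.

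**Conclusion.** The point holds as a matter of efficiency. At the planned effect, with a common ratio and a threefold HPV effect, the plain test gives about 78-84% power at the stated 190 against about 89-90% when stratified by HPV; at 229 the gain is about 5-9 points. With a twofold HPV effect it is about 2-4 points. If HPV-positive patients gain little or nothing (ratio 0.93-1.0), stratifying costs about 3-18 points at 229, most when few patients are HPV-negative.

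A reader might go further and conclude that the trial is underpowered, or that the stratified test is always stronger. The documents support neither conclusion: they do not give the trial's HPV mix or an HPV-positive effect, their Phase 2 remarks point both ways, and planned enrolment exceeds the stated 190. The absolute percentages are indicative only, since they assume exponential durations and ignore visit spacing. A stratified primary test is the reasonable default because the planning calculation specifies no HPV-specific effect and Protocol 4.5 reports consistency across HPV status. Confidence is medium.

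**What to change.** Before unblinding, and decided by staff blinded to treatment:

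- In SAP 9.1, specify a log-rank test stratified by HPV status and gastrostomy tube as recorded at randomisation, leaving site out. Carry it to 9.2 and 9.4.2, and write it separately into 9.4.3. Align the protocol synopsis and 12.1.
- Keep the unstratified log-rank as a named sensitivity analysis. Report a Cox hazard ratio stratified the same way, and the effect by HPV status.
- State the known downside: lower power if benefit is concentrated in HPV-negative patients.
- Check consistency with the test used at any interim look. If that look already fixes the plain test as primary, keep it, say why, and make the stratified test the named sensitivity analysis.

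The cost is wording in both documents, the interim check and one strata statement in the program. HPV status and tube are already collected, so no new data or patients are needed. The statistical price is the 3-18 points given in the verdict, should the effect prove to be concentrated.

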#### 9.2 SENSITIVITY ANALYSIS OF PRIMARY ENDPOINT

The same statistical method as for primary analysis will be used for sensitivity analysis, however, duration of SOM will be calculated from the first time the patient has a SOM to the last time the patient has a SOM. For statistical reasons, patients who do not experience SOM will be treated as having a duration of 0.01 days.

Possible scenarios for onset of SOM are displayed below in Figure 3, along with the duration of SOM.

Time point 2 Time point 3 6-week post-RT Duration of SOM

Time point 3 minus Time point 1 (event)

6-week post-RT minus Time point 1 (censored)

1 day (event)

1 day (event)

0.01 days (event)

Figure 3: Duration of SOM (Sensitivity Analysis)

#### 9.3 ANALYSES OF SECONDARY ENDPOINTS

## 9.3.1 Hierarchical Secondary Endpoints

Multiple endpoints in this trial are expected to be clinically important. To control type 1 error, the following five secondary endpoints will be tested in a fixed sequence, hierarchical test procedure. In this procedure, a sequential comparison of the groups for each endpoint will be calculated with unadjusted p-values. If the test is statistically significant, the null-hypothesis that the groups are the same will be rejected and testing of the next endpoint will be done. Once an analysis has a p-value above the threshold, no further endpoints will be formally tested. All 5 analyses will be conducted in the mITT population. The hierarchical orders of these endpoints are:

- 1. Comparison of the AUC for SOM (WHO Grade >3) by time plot (severity-weighted duration)
- 2. Comparison of the AUC for UOM (defined as WHO Grade ≥2) by time plot (severity-weighted duration)
- 3. Comparison of the incidence of SOM
- 4. Comparison of the quality of life assessment using the EORTC QLQ-C30 and QLQ-H&N43 instrument
- 5. Comparison of the total amount of opioids used

#### 9.3.2 Other Secondary Endpoints

- Comparison of the cumulative number of days of RT breaks (mITT population)
- Comparison of the duration of SOM; in all randomized patients receiving fractionated RT and concomitant cisplatin chemotherapy, given as 80-100 mg/m² (ITT population)
- Comparison of the duration of UOM (mITT population)
- Comparison of the cumulative amount of pain reported by patients (mITT population)

#### 9.4 ENDPOINT CALCULATIONS

The procedures for calculating these endpoints are given below.

## 9.4.1 Severity-weighted Duration of OM (Area-Under the OM-Time Curve)

The severity-weighted duration of OM (either SOM or UOM) will be calculated by the AUC of the OM versus time curve. This will be calculated by the formula from baseline ( $t_a$ ) to the time of the last reported WHO score recorded ( $t_b$ ):

$$AUC(t_b - t_a) = \sum_{i=a}^{b-1} \frac{(y_i + y_{i+1})(t_{i+1} - t_i)}{2}$$

where  $t_i$  represents the date of the ith WHO assessment, and  $y_i$  represents the value of the ith WHO assessment for WHO assessments for which the score is  $\geq 3$  (for SOM) or  $\geq 2$  (for UOM). The WHO score for the (i+1)th assessment does not need to be  $\geq 3$  (for SOM) or  $\geq 2$  (for UOM) but will be assigned a value of 0 if it is  $\leq 3$  (for SOM) or  $\leq 2$  (for UOM). If a patient experiences SOM or UOM at the 6-week post-RT visit (the last time point at which OM is measured), the AUC of that visit will be counted as 0. The AUC of SOM or UOM will be compared between treatment groups using a one-way ANOVA test.

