7.3. Patient Withdrawal Criteria

Patients have the right to withdraw from this trial at any time (as described in the informed consent document) without prejudice to further care. An investigator may withdraw a patient from the study at any time for any of the following reasons:

- The patient withdraws his/her consent or refuses follow-up evaluations.
- The patient is lost to follow-up and will not attend further study visits.
- The investigator determines that further participation would be detrimental to the patient's health or well-being.
- The patient fails to comply with the study requirements to cause harm to self or seriously interfere with the validity of the study results.
- The female patient becomes pregnant during the treatment period. In this case, treatment should be halted and the patient followed until the end of the pregnancy. If a child is born, the infant should be followed through at least 6 months of age.
- At the discretion of the site investigator if he/she feels that it is in the best medical interest of the patient.
- The patient misses more than 5 consecutive scheduled RT sessions.
- Patients withdrawn from the study will have as many of the trial assessments completed
 as the patient permits including blood tests and scans but not including OM scoring. All
 other therapies including radiation therapy, the type and frequency of chemotherapy, and
 oral treatments will remain at the discretion of the clinical team. Patients will be censored
 in the efficacy analyses at the time of withdrawal.
- Patients withdrawn from the trial will not be replaced but enrollment will continue until a minimum of 260 patients have been enrolled.

7.4. **Termination of the Study**

The study may be terminated early for any of the following reasons:

- A health authority or DMC requests termination of the study.
- It has been determined that the risk level associated with the experimental drug is significant and warrants termination of the study.
- Soligenix, for reasons other than safety, may terminate the study at any time by written notice of intended termination provided at least thirty (30) days prior to termination.
- The investigator or IRB/EC, for reasons other than safety, may terminate participation of this site in the study by written notice of intended termination provided at least thirty (30) days prior to termination.

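### Both gated AUC endpoints stop at the last recorded WHO score, so an mITT patient who leaves with ongoing severe mucositis gets a falsely low score

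*SAP*

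**What the plan says.** - **End of the window.** SAP 9.4.1 applies a trapezoid rule from baseline "to the time of the last reported WHO score recorded". It gives no common end, no scaling for time observed and no imputation. Its only rule about the end of observation concerns a patient still affected at the planned last visit: "the AUC of that visit will be counted as 0".
- **Test.** "The AUC of SOM or UOM will be compared between treatment groups using a one-way ANOVA test". The protocol synopsis had named another method: "A log-rank test will be used to compare the AUC of the WHO Grade-time curve". Protocol 12.1 says the same.
- **Who is included.** SAP 9.3.1: "All 5 analyses will be conducted in the mITT population". SAP 3.2.3 admits any randomized patient with one dose and 55 Gy, so leaving after 55 Gy does not remove a patient.
- **After withdrawal.** Protocol 7.3 asks for remaining assessments "as the patient permits including blood tests and scans but not including OM scoring", and says that leavers are censored in the efficacy analyses when they withdraw.
- **Duration endpoints.** SAP 9.1 and 9.4.3 censor an unresolved episode at discontinuation. Appendix 1.4 adds two sensitivity analyses (last grade held for the whole trial; grade 0), under a heading limited to SOM duration.
- **Place in the sequence.** AUC for SOM is first and AUC for UOM second of five ordered secondaries. SAP 9.3.1: "Once an analysis has a p-value above the threshold, no further endpoints will be formally tested".

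**The concern.** A log-rank analysis with censoring uses only the time observed. ANOVA on a raw sum has no such device: it takes the truncated area as the patient's complete result. Every severe day after leaving then counts as zero, and a patient with a bad course can score better than a milder patient who stayed.

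These two endpoints control the rest of the secondary sequence. A false pass would support a claim on severity-weighted duration. A false failure would stop formal testing of SOM incidence, quality of life and opioid use.

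**Working it through.** **Plan's own figure.** The documents give no mean, standard deviation or power for either AUC. The only size calculation is for the primary log-rank test (medians 13 v 8 days, 90% power, two-sided 0.05, 95 per arm). It reproduces: hazard ratio 8/13 = 0.615, and Freedman's formula gives 186 events against 190 patients. It serves here only as a source of inputs.

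**Time that can be lost.** 55 Gy takes 28 fractions at 2.0 Gy (5.6 weeks at five a week) or 25 at 2.2 Gy (5.0 weeks). On a 7-week course at 2.0 Gy, scoring runs to week 7 + 6 = 13, so up to 13 - 5.6 = 7.4 weeks can go unscored in an mITT patient.

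**Worked patients.** Visits are every 3.5 days to day 63, then weekly to day 91. Each interval that starts at or above the threshold adds (y_i + y_{i+1}) x days / 2, with y_{i+1} set to 0 if it is below the threshold.

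- Grade 3 for 21 days: five full intervals, 5 x 3 x 3.5 = 52.5, plus the closing one, (3 + 0) x 3.5 / 2 = 5.25; total **57.75**.
- Same patient leaving after 7 days: 2 x 3 x 3.5 = **21**, which is 64% lower.

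A longer assumed course has grade 2 from day 14, grade 3 from day 28 to 70, and grade 2 to day 84:

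| Handling | SOM AUC | UOM AUC | SOM AUC / days followed |
|---|---|---|---|
| Followed to day 91 | 115.5 | 173.25 | 115.5/91 = 1.27 |
| Leaves at day 42 with grade 3 (current rule) | 42.0 | 71.75 | 42/42 = 1.00 |
| Leaves at day 42, last grade held to day 91 | 189.0 | 218.75 | 189/91 = 2.08 |
| Milder completer, grade 3 on days 28-49 only | 57.75 | 115.5 | 57.75/91 = 0.63 |

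Under the current rule the leaver beats the milder completer on both endpoints. Dividing by follow-up restores the SOM order.

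**Group level, no true effect.** All leaving rates and courses below are assumptions. ANOVA with two groups is the t-test.

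- *Model A*: 114 per arm, 85% with SOM, exponential duration with median 13 days, 25% at grade 4, leaving time uniform within the episode.
- *Model B*: 95 per arm, 30% never with SOM, grade 3 throughout, onset day 21-42, overall median duration 13 days, leaving only while severe and from about day 38.
- *Model C*: a third set of assumptions, 114 per arm.

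| Leaving mid-SOM | Model | Mean AUC, second arm | Two-sided rejection |
|---|---|---|---|
| Equal, 5% to 16% | B | no shift | 5.2-5.3% |
| 5% v 15% | A | -5% | about 6% |
| 5.4% v 16% | B | about -5 grade-days | 8-9% |
| 5% v 15% | C | -8% | about 8% |
| 5% v 25% | A | -10% | 11-12% |
| 5% v 25% | C | -16% | about 17% |

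For Model B, the rate is ln(0.7/0.5)/13 = 0.0259 per day, so the uncapped mean is 38.6 days. Capped at 91 - 31.5 = 59.5 days it is 38.6 x (1 - e^-1.54), about 30.3 days. Mean AUC is then 3 x 0.7 x 30.3, about 64, and 5/64 is about 8%. In the mildest variant (Model A with leaving only after about day 38), 5% v 15% gave 5.4%.

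**Group level, planned effect (Model B, 13 v 8 days).** The true AUC difference is about 17.8.

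| Leaving, placebo / SGX942 | Difference read | Power, full follow-up | Power, current rule |
|---|---|---|---|
| 16% / 14% | 15.3 | 50% | 45% |
| 5% / 14% | 20.4 | 51% | 67% |
| 16% / 5% | 11.9 | 52% | 29% |

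**Candidate remedies, no true effect, 5% v 15%.** In Model C, holding the last grade to six weeks post-RT turned -8% into +18% and raised rejection from about 8% to 17% (17% to 51% at 5% v 25%). Model B gave 10% and Model A 26%. Dividing by days of follow-up cut the Model C bias to about -4% and rejection to about 5%.

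**The case against.** **General text exists.** Appendix 1.5 refers to a last-value-forward method and promises sensitivity analyses of secondary endpoints. SAP 9 repeats the efficacy analyses in ITT and PP, and Protocol 7.3 censors leavers. So it would be too strong to infer that the plan ignores early leaving. But none of this reaches 9.4.1, which fixes the end of the AUC explicitly. The Appendix 1.5 analyses are unspecified and tied to the pandemic. ITT uses the same truncated formula. PP may exclude some leavers through its dosing rules but does not complete their scores. ANOVA cannot apply the censoring rule.

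**The error rates are invented.** This stands in part. No rate of leaving after 55 Gy is given, and a three- to five-fold imbalance between arms has no stated basis. The figures show sensitivity; they are not forecasts. A reader might also infer that the false-positive rate doubles. That describes one tail only (4.9-5.7% against 2.5% at 5% v 15% in Model A). SAP 3.3 makes tests two-sided at 5%, and on that scale the rise is smaller.

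**Restore the log-rank test.** The change of test between protocol and SAP is a separate discrepancy. Reverting would not fully cure this one: on the AUC scale a patient with a higher grade accumulates area faster and is censored at a higher value, so the censoring is informative.

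**The onset interval.** A reader might add that the formula counts no area on the interval in which SOM begins. That rule applies alike in both arms, matches the primary definition's start at the first score of 3 or more, and creates no bias from leaving. It is not part of this point.

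**Conclusion.** The point holds for patients who reach 55 Gy and then leave while severe (SOM) or ulcerated (UOM). Those who stop RT before 55 Gy are outside mITT. For an individual the error is large: about a third of the full SOM score remains in both worked cases (21/57.75 and 42/115.5, each 36%).

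For the comparison, the size depends on leaving rates that the documents do not give. Equal leaving keeps type I error near 5% and shrinks a real difference. Unequal leaving moves the result toward the arm that loses more severe patients: about 5-8% of mean AUC with 6-9% two-sided rejection at 5% v 15%, and about 10-16% with 10-17% at 5% v 25%.

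A reader might infer that the rule favours SGX942. The documents do not support a direction; it depends on which arm loses more severe patients. Nor is the primary endpoint affected, since it censors leavers. The matter should be corrected because the secondary sequence passes through these two tests, but it does not undermine the main result.

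**What to change.** In SAP 9.4.1, before unblinding:

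1. Define both AUCs from baseline to a common end, the 6-week post-RT visit.
2. State one main rule for unobserved time after leaving: either multiple imputation of WHO grades at the missed visits, or AUC divided by days of follow-up.
3. Extend the two Appendix 1.4 analyses (last grade held to the end; grade 0 after leaving) to both AUCs, as sensitivity bounds.
4. Say whether the last-value-forward remark in Appendix 1.5 applies to the AUC, so that two analysts would compute the same value.

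Last grade carried forward should not be the main analysis. In the worked patient it gives 189 against a true 115.5, an error of +73.5 that mirrors the current -73.5 (42 - 115.5), and in the simulations with unequal leaving it raised false rejection above the current rule's.

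The cost is SAP wording and modest extra programming, with no new visits or data. Multiple imputation brings reliance on its model. Dividing by follow-up is simpler but left a bias of about -4% in the simulation above.
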